9.1. Adverse events

The adverse event types include:

- **Pre-treatment adverse events** are adverse events that developed or worsened or became serious during the pre-treatment period.
- **Treatment-emergent adverse events** are adverse events that developed or worsened or became serious during the TEAE period.
- **Post-treatment adverse events** are adverse events that developed or worsened or became serious during the post-treatment period. AEs categorized as post-treatment AEs (following the rules specified below) will not be summarized.

The primary focus of adverse event reporting will be on TEAEs. Pre-treatment adverse events will be summarized separately.

All AEs will be coded by LLT, PT, HLT, HLGT, and associated primary SOC using the version of Medical Dictionary for Regulatory Activities (MedDRA) currently in effect at Sanofi at the time of each database lock.

Adverse events will be recorded from the time of signed informed consent until the end of the study or the resolution/stabilization of all SAE and AESI.

If an adverse event date/time of onset (occurrence, worsening, or becoming serious) is incomplete, an imputation algorithm will be used to classify the adverse event as pre-treatment, treatment-emergent, or post-treatment. The algorithm for imputing date/time of onset will be conservative and will classify an adverse event as treatment-emergent unless there is definitive information to determine it is pre-treatment or post-treatment. Details on classification of adverse events with missing or partial onset dates are provided in [Section 15.4.5](#).

Adverse events will be summarized by primary SOC, HLGT, HLT, and PT, sorted by internationally agreed order of primary SOC and then alphabetically for the other levels, for each study intervention group using number and percentage of participants experiencing an adverse event. Multiple occurrences of the same event in the same participant will be counted only once in

the tables within an observation period (pre-treatment period or TEAE period). The denominator for computation of percentages will be the safety analysis set within each study intervention group. Participants experiencing asthma exacerbations will be further summarized using the LLT level as appropriate within adverse event summaries.

Sorting within tables ensures the same presentation for the set of all adverse events within the observation period (pre-treatment, treatment-emergent). For that purpose, the table of all treatment-emergent adverse events presented by primary SOC and PT (sorted by the internationally agreed SOC order and decreasing frequency of PTs within SOCs in the dupilumab group) will define the presentation order for all other summaries unless otherwise specified. In case of equal frequency regarding PTs, alphabetical order will be used.

On top of the analysis planned below, all TEAEs, all treatment emergent SAEs, TEAEs leading to permanent study intervention discontinuation and TEAEs leading to death will be summarized by study intervention group and repeated on the subgroups of safety participants according to trial impact (disruption) due to COVID-19 pandemic.

Overview summary of the number and percentages of participants within the following categories will be provided by study intervention group:

- Any TEAE
- Any study intervention related TEAE
- Any severe TEAE
- Any serious TEAE
- Any TEAE leading to permanent study intervention discontinuation
- Any TEAE of special interest
- Any serious TEAE of special interest
- Any TEAE leading to death

The overview summary for TEAEs will be provided on the safety set and will be repeated on the subgroups of safety participants according to trial impact (disruption) due to COVID-19 pandemic.

Additionally, an overview of pre-treatment AEs will be presented using similar categories including:

- Any AE
- Any Severe AE
- Any Serious AE
- Any AESI
- Any Serious AESI
- Any AE leading to death

Individual listings (AEs, SAEs, TEAEs leading to permanent study intervention discontinuation, AEs leading to death, AESI and all AEs in treated but not randomized participants (where such participants are recorded in the study)) will be provided to support the summary tables based on the safety set.

Additionally, any defect in the IMP will be reported as soon as possible by the Investigator to the monitoring team that will complete a product complaint form within required timelines.

Appropriate information (e.g., samples, labels or documents like pictures or photocopies) related to product identification and to the potential deficiencies may need to be gathered. The Investigator will assess whether the quality issue must be reported together with an AE or SAE.

No analysis of these data is foreseen. Reporting of these information falls beyond the scope of this SAP.

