4 STUDY DESIGN

4.1 OVERALL DESIGN

This is a Phase 4 randomized, multinational study with a 24-week double-blind placebo-controlled period to explore the effect of dupilumab on airway inflammation through assessments of biomarkers, mucus plugging, and other lung imaging parameters in participants with asthma.

Study participation for each participant will be a total of minimum 29 weeks and up to 41 weeks.

The study includes 3 study periods:

- Screening period: 4 weeks (± 1 week), from signed informed consent to randomization.
- Randomized, placebo-controlled treatment period: 24 weeks from baseline (Day 1).
- Post treatment follow-up period: up to 12 weeks or until the participants switch to commercialized dupilumab (or other biologic products), whatever comes first.

Participants who fulfill the inclusion criteria and do not meet any of the exclusion criteria will be randomized (2:1) to one of the following investigational medicinal products (IMP).

- Dupilumab: participants will receive a loading dose of 600 mg of dupilumab (2 x 300 mg dupilumab SC on Day 1, followed by 300 mg every 2 weeks (Q2W) for 24 weeks.
- Placebo: participants will receive 2 x 2 mL placebo injections SC on Day 1, then 1 placebo injection Q2W for 24 weeks.

Randomization will be stratified by ICS dose level (medium/high- no less than 40% in 'high ICS' stratum) and region (Eastern Europe/ROW). In total, no more than 40% participants should be in "Eastern Europe" strata.

Study intervention discontinuation follow-up

Participants who prematurely discontinue the study intervention (prior to completing the 24-week treatment period) should attend an Early Treatment Discontinuation (ETD) visit at the earliest convenience with all the assessments planned for the End of Treatment (EOT) visit (V5), except HRCT and IMP. In particular cases when the ETD visit is close to a regular study visit, ETD could be merged and will replace the regular visit (See [Section 7.1.1](#)).

In addition, the participants will be asked and encouraged to complete all the remaining study visits according to the visit schedule until and including the EOT visit (V5).

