9.4.2 Safety analyses

All safety analyses will be performed on the safety population and will be presented by treatment group.

The treatment-emergent is defined as the period of time from the date and time of the first dose of IMP through the date of last dose + 12 weeks (or the day before switch to commercialized dupilumab or other biologic treatment, whichever occurs first).

Table 8 - Safety analyses

Endpoint	Statistical Analysis Methods
Secondary	
 Incidence of TEAEs, TESAEs, TEAE leading to study intervention discontinuation and AESI Adverse event incidence tables will be presented by system organ class (SOC) (sorted by internationally agreed order), high-level group term (HLGT), high level term (HLT) and preferred term (PT), the number (n) and percentage (%) of participants experiencing an AE. Multiple occurrences of the same event in the same participant will be counted only once in the tables. The denominator for computation of percentages is the safety population within each treatment group. Proportion of participants with at least one TEAE, serious TEAE, AESI, and TEAE leading to discontinuation of the study intervention will be tabulated by treatment group. In addition, TEAEs will be described according to maximum intensity and relation to the study drug. Serious AEs and AEs leading to study discontinuation that occur outside the treatment-emergent period will be summarized separately.

Multiplicity Considerations for the secondary endpoints

A multiplicity control procedure and the selected list of secondary endpoints to be tested in the hierarchical order will be specified in the Statistical Analysis Plan. Regardless of eligibility to be declared significant, results for all comparisons will be presented. Descriptive statistics including number of participants, mean, standard deviation, and LS means will also be provided.

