3. INVESTIGATIONAL PLAN

3.1. Overall study design and plan

This is a Phase IV, 2:1 randomized, parallel, multinational, multicenter study, with a 24-week double-blind placebo-controlled treatment period to assess the effect of dupilumab on airway inflammation through assessments of lung function, mucus plugging, and other lung imaging parameters in participants with asthma.

Approximately 97 participants will be randomly assigned to study intervention, in a 2:1 dupilumab to placebo ratio, such that approximately 87 evaluable participants complete the study, assuming a 10% dropout rate (approximately 58 in the active group and 29 in the placebo group). Randomization will be stratified by dose level (medium/high – no less than 40% in ‘high ICS’ stratum) of inhaled corticosteroids (ICS) and region (Eastern Europe (EE)/Rest of the World (ROW)). In total, no more than 40% participants should be in EE strata.

[figure not shown]
The study will comprise of:

- Screening period: 4 weeks (± 1 week), from signed informed consent to randomization (Day [-35, -21] to Day -1).
- Randomized, placebo-controlled treatment period: 24 weeks from baseline (Day 1).
- Post-treatment follow-up period: up to 12 weeks or until the participant switches to commercialized dupilumab (or other biologic product), whichever comes first.

Study duration for each participant will be a total of minimum 29 weeks and up to 41 weeks. A participant is considered to have completed the study if he/she has completed all phases of the study including the post treatment follow-up visit (V6).

The end of the study is defined as the date of the last visit of the last participant in the study.

Figure 3-1 Study plan

ACQ-7= 7-item Asthma Control Questionnaire; AQLQ(S) =Asthma Quality of Life Questionnaire with Standardized Activities; D=Day; FeNO= Fractional exhaled nitric oxide; FU= Follow-up; HRCT= High-resolution computed tomography; ICF=Informed Consent Form; mg=milligram; mL=milliliter; Q2W= every 2 weeks; R=Randomization; V=Visit

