7.2.1. Extent of exposure

The extent of IMP exposure will be assessed by the duration of IMP exposure.

Duration of IMP exposure is defined as last IMP administration dose date – first IMP administration dose date +14 days, regardless of unplanned intermittent discontinuations.

Duration of IMP exposure will be summarized descriptively as a quantitative variable (number, mean, SD, median, Q1, Q3, minimum and maximum). In addition, duration of IMP exposure will also be summarized categorically by numbers and percentages for each of the following categories:

- >0 and \leq 2 weeks
- >2 and \leq 4 weeks
- >4 and \leq 8 weeks
- >8 and \leq 12 weeks
- >12 and \leq 16 weeks
- >16 and \leq 20 weeks
- >20 and \leq 24 weeks
- >24 and \leq 26 weeks
- >26 weeks

and cumulatively according to the following categories:

- \geq 1 day
- >2 weeks
- >4 weeks
- >8 weeks
- >12 weeks
- >16 weeks
- >20 weeks
- >24 weeks
- >26 weeks

Additionally, the sum of the duration of IMP (total) exposure for all participants will be summarized by study intervention group and will be expressed in participant years.

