9. SAFETY ANALYSIS

All safety results will be summarized using the safety set by actual study intervention group.

The observation periods include:

- The **pre-treatment** period is defined as the time from the signed informed consent date up to first administration of the IMP.
- The **treatment-emergent adverse event (TEAE)** period is defined as the time from the first administration of the IMP (on Day 1) to the last administration of the IMP +98 days and up to the end of the study follow-up.
- The **post-treatment** period is defined as the time starting 1 day after the end of the TEAE period up to the end of the study follow-up.

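### TEAE incidence is given only as crude percentages over a window that closes at a biologic switch, so any difference in switching between arms would distort the comparison unseen

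*SAP*

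**What the plan says.** SAP 9.1 summarises adverse events "using number and percentage of participants experiencing an adverse event" and adds: "The denominator for computation of percentages will be the safety analysis set within each study intervention group". Protocol 9.4.2 (Table 8) prescribes the same measure and denominator. SAP 9.1 to 9.1.9 plan no adverse-event table limited to a fixed window, no rate per time at risk and no time-to-first-event summary.

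The treatment period is the same in both arms (SAP 3.1): "Randomized, placebo-controlled treatment period: 24 weeks from baseline (Day 1". What follows it is not. Follow-up lasts "up to 12 weeks or until the participant switches to commercialized dupilumab (or other biologic product), whichever comes first" (SAP 3.1; protocol 4.1 has the same rule).

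The protocol ends the treatment-emergent period explicitly at the switch: from first dose "through the date of last dose + 12 weeks (or the day before switch to commercialized dupilumab or other biologic treatment, whichever occurs first" (9.4.2). SAP 9 runs the period from first dose "to the last administration of the IMP +98 days and up to the end of the study follow-up". It does not name the switch there, but SAP 3.1 ends follow-up at the switch, so in practice the window stops there under either document.

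SAP 7.2.1 totals IMP exposure, which "will be expressed in participant years". That is dosing time (first to last dose plus 14 days), and it is not used as an adverse-event denominator.

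**The concern.** A crude percentage is comparable between arms only if the arms are watched for similar lengths of time. Here two treatment completers can differ by up to 12 weeks of observation, and the cause of the difference is a treatment decision taken after randomization. Protocol 6.5 leaves asthma treatment in follow-up to the investigator's judgment, and inclusion criterion I 03 requires uncontrolled asthma at entry. It is therefore plausible that the decision to start a commercial biologic depends on how the participant has responded, and so on arm.

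The incidence of TEAEs, SAEs and AESIs is the trial's safety endpoint (protocol Table 1), and readers will compare the two columns. If one arm is watched longer, it shows more participants with events at the same underlying rate.

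The imbalance would also go unseen. Protocol 4.4 counts a participant as a completer once Visit 6 is done, and the Schedule of Activities places Visit 6 before the first commercial injection for anyone who switches. Switchers who make that call therefore count as completers. The disposition list in SAP 5.1 has no line for switching or for length of follow-up.

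**Working it through.** **Window length.** Total participation is stated as 29 to 41 weeks. With the longest screening period (5 weeks), 5 + 24 + 0 = 29 and 5 + 24 + 12 = 41, so both limits reproduce. Post-baseline time for a treatment completer is then 24 weeks (switch at once) to 36 weeks (no switch), a ratio of 36/24 = 1.5. Three qualifications apply:
- With 3-week screening the total would be 3 + 24 + 0 = 27, so 29 is not a strict minimum.
- If the last dose is at Week 22, the protocol's period ends at 22 + 12 = 34 weeks and the SAP's at 22 + 14 = 36 weeks.
- 24 weeks is not a floor for everyone. Under the SAP's 98-day (14-week) rule, a last dose before Week 24 − 14 = 10 gives a window shorter than 24 weeks, as does leaving the study early.

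**Assumptions, since the documents give no adverse-event rate and no switching rate.** The event rate is constant and equal in both arms, all switches occur at Week 24, and the other completers are observed to Week 36. Let p24 be the 24-week risk and s the share of an arm that switches.

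- p36 = 1 − (1 − p24)^1.5
- crude percentage = s × p24 + (1 − s) × p36
- false difference, dupilumab minus placebo = (s_placebo − s_dupilumab) × (p36 − p24)

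**One case in full.** With p24 = 40%, p36 = 1 − 0.6^1.5 = 53.5%. Let 60% switch on placebo and 30% on dupilumab.
- Placebo: 0.6 × 40 + 0.4 × 53.5 = 45.4%.
- Dupilumab: 0.3 × 40 + 0.7 × 53.5 = 49.5%.
- False difference: 4.1 points.
- Mean observation: 0.6 × 24 + 0.4 × 36 = 28.8 weeks against 0.3 × 24 + 0.7 × 36 = 32.4 weeks, a ratio of 1.125.

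**Range (false difference in percentage points).**

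| p24 | p36 | 40% vs 30% switch | 60% vs 30% | 100% vs 0% | equal |
|---|---|---|---|---|---|
| 5% | 7.4% | 0.2 | 0.7 | 2.4 | 0 |
| 40% | 53.5% | 1.4 | 4.1 | 13.5 | 0 |
| 50% | 64.6% | 1.5 | 4.4 | 14.6 | 0 |
| 60% | 74.7% | 1.5 | 4.4 | 14.7 | 0 |
| 70% | 83.6% | 1.4 | 4.1 | 13.6 | 0 |

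Swapping the arms reverses the sign. The last unequal column is the extreme, not an expectation.

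**Against sampling error.** With about 97 randomized 2:1 (about 65 and 32), the 95% half-width for a difference in percentages is 196 × √[p36(1 − p36)(1/65 + 1/32)]. That is 21.1 points at p36 = 53.5%, 15.7 at 83.6% and 11.1 at 7.4%.

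**With person-time.** Under a constant rate, the expected number of participants with an event equals the rate times the expected time at risk to first event or censoring. The expected rate ratio is then 1 in every row, whatever the switching.

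**The case against.** The strongest reply is that the bias is hypothetical. Neither document gives a switching rate or a difference by arm, participants and investigators are blinded, and the synopsis ties post-trial access to country requirements rather than to response. This stands. A reader might infer that the safety comparison is biased as planned; the documents support only that it would be if switching differed by arm.

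Second, the safety analysis is descriptive, with no test or confidence interval on adverse events, and the SAP follows the protocol's own Table 8. Closing the window before the switch also keeps events on commercial drug out of the randomized comparison. All true, and a reason to leave the main tables as they are. It does not make unequal windows comparable.

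Third, the size is modest. A 1- to 4-point shift is well inside the sampling error above, and one placebo participant of about 32 is already 3.1 points. The model also puts every switch at the earliest time and carries the on-treatment event rate into a tail whose only scheduled contact is one telephone visit. This limits the importance of the point, but a systematic shift adds to the noise and the plan offers no way to see it.

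Fourth, a reader might infer that every TEAE table is affected. That goes too far: TEAEs leading to IMP discontinuation cannot arise in the off-treatment tail of completers, who have no IMP left to stop. Nor does the SAP already hold the right denominator, because the participant-years in 7.2.1 are dosing time, not time under observation.

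Finally, the individual listings with study day let a reader find events after Week 24. They do not show how long participants without events were watched.

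**Conclusion.** The point holds in conditional form. TEAE incidence is planned only as a crude percentage, over a window that for treatment completers varies by about 12 weeks and closes at the biologic switch, and no planned output would reveal a difference in switching. If switching does differ, the comparisons of any TEAE, serious TEAEs and AESIs are distorted, in a direction that cannot be known in advance.

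On the assumptions above, the distortion is about 1 to 4 points for common events (24-week risk of 40% to 70%) when switching differs by 10 to 30 points, 0.2 to 0.7 points for an event with 5% risk, and zero with equal switching. This is a cheap improvement, not a flaw that undermines the safety assessment.

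The point is separate from the mismatch between the protocol's 12 weeks and the SAP's 98 days. Those two definitions need to be reconciled, but agreeing an end date would not equalise the observed time.

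**What to change.** Keep the protocol's treatment-emergent period for the main tables and add three items to SAP 9.1:

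1. An overview of any TEAE, serious TEAEs and AESIs from Day 1 to the Week 24 visit (or study withdrawal) for all safety-set participants. Do not cut early stoppers at last dose plus 14 days. They are asked to attend through Visit 5, and a cut tied to dosing would make the window unequal again. State that, for very early stoppers, this window can extend past the formal treatment-emergent period.
2. Participants with an event per 100 participant-years over the full treatment-emergent period. Person-time runs from first dose to the earliest of first event, biologic switch, and the end of the treatment-emergent period or follow-up. Do not use the IMP exposure of SAP 7.2.1. State that these rates remove the effect of unequal follow-up only if the event rate is roughly constant on and off treatment.
3. By arm, the number and timing of switches and the length of treatment-emergent observation. Neither document specifies a field for the switch date, so use the Visit 6 date if none is recorded.

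The cost is SAP wording and a few extra safety tables. The protocol's definition of the treatment-emergent period does not change.

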9.1.1. Incidence of adverse events

The following TEAE summaries will be generated for the safety analysis set, for each study intervention group.

- All TEAEs presented by primary SOC, HLGT, HLT, and PT, showing the number and percentage of participants with at least 1 TEAE
- All TEAEs presented by primary SOC, showing number and percentage of participants with at least 1 TEAE, sorted by the internationally agreed primary SOC order
- All TEAEs presented by PT, showing number and percentage of participants with at least 1 TEAE, sorted by decreasing incidence of PT in the Dupilumab group
- All pre-treatment AE presented by primary SOC and PT, showing number and percentage of participants with at least 1 pre-treatment AE
- All TEAEs presented by primary SOC and PT, showing number and percentage of patients with at least 1 TEAE
- All treatment-emergent COVID-19 related adverse events presented by primary SOC and PT, showing number and percentage of participants with at least 1 treatment-emergent COVID-19 related AE
- Common TEAEs (PTs with an incidence $\geq 5\%$ in any study intervention group) by primary SOC, HLGT, HLT, and PT

Search criteria for COVID-19 related AE will be provided by SANOFI.

9.1.2. Relationship of adverse events to study intervention

The following TEAE summary will be generated.

- All TEAEs by relationship, presented by primary SOC, HLGT, HLT and PT, showing the number and percentage of participants with at least 1 TEAE

9.1.3. Severity of adverse event

The following TEAE summary will be generated.

- All TEAEs by maximal severity, presented by primary SOC and PT, showing the number and percentage of participants with at least 1 TEAE by severity (ie, mild, moderate, severe).

9.1.4. Serious adverse events

The following TEAE summaries will be generated.

- All serious TEAEs presented by primary SOC, HLT, HLT and PT, showing the number and percentage of participants with at least 1 serious TEAE.
- All serious TEAEs by relationship, presented by primary SOC, HLT, HLT and PT, showing the number and percentage of participants with at least 1 serious TEAE.

